7.2 Expedited reporting by investigator to Helsinn Healthcare SA

Serious adverse events (SAE) are defined above. The investigator will inform Helsinn Healthcare SA of any SAE within 24 hours of being aware of the event via email and/or fax.

All pregnancies will also be reported.

The following SAEs are not subject to expedited reporting, but will be included in the annual report via the SAE log.

- a. Infection or cytopenias leading to hospitalization or prolongation of hospitalization; disease progression leading to death; life-threatening AE, hospitalization or prolongation of hospitalization, or disability.

Adverse events will be documented in the medical record and entered into the case report form. PDMS/CORe will be used as the electronic case report form for this protocol. Investigator or physician designee is responsible for verifying and providing source documentation for all adverse events and assigning the attribution for each event for all subjects enrolled on the trial. This form must be completed and supplied to Helsinn Healthcare SA within 24 hours/1 business day at the latest on the following working day. The initial report must be as complete as possible, including details of the current illness and (serious) adverse event, and an assessment of the causal relationship between the event and the investigational product(s). Information not available at the time of the initial report (e.g., an end date for the adverse event or laboratory values received after the report) must be documented on a follow-up MDACC SAE reporting form.

Pregnancies and suspected pregnancies (including a positive pregnancy test regardless of age or disease state) of a female subject or the female partner of a male subject occurring while the subject is on study drug, or within 30 days of the subject's last dose of study drug, are considered immediately reportable events. Study drug is to be discontinued immediately in a female patient and the patient instructed to return any unused portion of the study drug to the investigator(s). The pregnancy, suspected pregnancy, or positive pregnancy test must be reported to Helsinn Healthcare SA immediately by phone and facsimile using the MDACC AE report form. The female should be referred to an obstetrician-gynecologist experienced in reproductive toxicity for further evaluation and counseling.

8.0 STATISTICAL CONSIDERATIONS

This is a single-center phase II trial designed to assess the effect of ruxolitinib in combination with pracinostat in subjects with Primary, Post Polycythemia Vera, or Post Essential Thrombocythemia Myelofibrosis (PMF, post-PV MF, or post-ET MF).

The primary objective is to assess efficacy in terms of the objective response rate (i.e., complete and partial response, and clinical improvement by IWG-MRT) in patients with MF. Secondary objective is to determine the safety of the combination therapy in this population.

Primary Endpoint is the objective response rate (ORR), defined as a clinical improvement (CI), partial remission (PR), and complete remission (CR) according to the International Working Group (IWG) Criteria. All subjects meeting the eligibility criteria that have signed a consent form and have begun treatment will be evaluable for response.

A total of 25 patients will be enrolled from MDACC and patients will be registered through the Clinical Oncology Research System (CORE). The estimated accrual rate is 2-3 patients per month. Initially patients will receive ruxolitinib alone for the first 3 cycles, where 1 cycle is 28 days (i.e., 4 weeks). Then, starting from cycle #4, patients will receive the combination therapy of ruxolitinib with pracinostat.

The method of Thall, Simon and Estey [1995] will be used for futility and toxicity monitoring for this study. For futility monitoring, the primary endpoint of interest is the objective response (OR) rate at the end of 6 treatment cycles. Patients who drop off the study early due to any reason will be counted as failures (i.e., non-responders). The target response rate is 50% and the following futility stopping rule will be applied $\text{prob}\{p(\text{OR}) < 0.5\} > 0.95$, where $p(\text{OR})$ denotes the objective response rate, with a beta (1,1) prior distribution. That is, the treatment will be stopped if during the study we determine that there is more than 95% chance that the OR rate is less than 50%.

For toxicity monitoring, we denote the probability of toxicity by $p(T)$, where toxicity is defined as Grade 3-4 clinically relevant non-hematologic toxicity or a serious adverse event that is at least possibly related to the study drug (Common Terminology Criteria for Adverse Events CTCAE version 4.0). We assume as a priori, $p(T) \sim \text{beta}(0.4, 1.6)$. We will stop treating patients if $\text{Pr}(p(T) > 0.20 | \text{data}) > 0.87$. That is, we will stop the trial for new patient enrollment if at any time during the study we determine that there is more than 87% chance that the toxicity rate is more than 20%. The OR rate and the toxicity will be monitored simultaneously using Bayesian stopping boundaries (Table 1) calculated based on beta-binomial distribution. Independence is assumed between OR and toxicity. Patients will be monitored in cohort size of 5, starting from the 5th patient. Multc Lean Desktop (version 2.1) was used to generate the futility/toxicity stopping boundaries and the operating characteristics table (Table 2).

Table 1: Stopping boundaries for OR and toxicity

Number of patients	Stop the trial if	Stop the trial if
--------------------	-------------------	-------------------

evaluated	there are this many OR patients	there are this many patients with toxicities
5	0	3-5
10	0-2	4-10
15	0-4	6-15
20	0-6	7-20

Table 2: Operating characteristics of the Bayesian futility and toxicity monitoring

True OR Rate	True toxicity Rate	Prob (stop the trial early)	Average sample size
0.3	0.1	0.69	15.7
	0.2	0.74	14.6
	0.3	0.84	12.4
	0.4	0.94	9.8
0.4	0.1	0.35	20.3
	0.2	0.46	18.6
	0.3	0.67	15.1
	0.4	0.88	11.3
0.5	0.1	0.13	23.1
	0.2	0.27	21.1
	0.3	0.56	16.8
	0.4	0.83	12.1
0.6	0.1	0.04	24.3
	0.2	0.2	22.1
	0.3	0.52	17.5
	0.4	0.82	12.5

Statistical Analysis Plan

Summary statistics will be provided for continuous variables. Frequency tables will be used to summarize categorical variables. The objective response rate (ORR) will be estimated along with the Bayesian 95% credible interval. Data from all subjects who receive any study drug will be included in the safety analyses. The severity of the toxicities will be graded according to the NCI CTCAE v4.0 whenever possible. We will follow standard reporting guidelines for adverse events. Safety data will be summarized by category, severity and frequency. The proportion of patients with AEs will be estimated, along with the Bayesian 95% credible intervals.

Duration of response: Duration of response is defined as the date at which the subject's objective status is first noted to be a CR, PR or CI to the date of progression (no longer meeting criteria for either CR, PR or CI) is documented (if one has occurred). Patients who continue to respond as of the data cut-off date will be censored as of the date of their last assessment documenting continued response.

Time to response: The time to response is defined as the time from study registration to the first date at which the subject's objective status was classified as a response (CR, PR or CI). In subjects who do not achieve a response, time to response will be censored at the subject's last evaluation date.

The distribution for each of these event-time variables (duration of response and time to response) will be estimated by Kaplan-Meier curves.

Anemia: Descriptive statistics will be used to explore improvements in anemia and transfusion dependence. The following outcomes will be summarized: mean changes in hemoglobin at monthly intervals. The proportion of transfusion independent patients not requiring transfusions on study who experience an increase of 2 g/dL in their hemoglobin relative to baseline, the proportion of transfusion dependent patients (defined as requiring a transfusion of 2 units PRBCs monthly for 3 months (12 weeks) prior to starting the trial) who become transfusion independent (not requiring a transfusion of PRBCs over a period of 3 months (12 weeks) while on study), the proportion of transfusion dependent patients who become transfusion independent and have a 1 g/dL increase in hemoglobin relative to baseline, and the proportion of transfusion independent patients requiring a transfusion while on study.

JAK2V617F Allele burden: Change in JAK2V617 allele burden from baseline to each visit where it is measured.

Correlative Studies: Descriptive statistics will be applied to the analysis of these findings.

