1.0 HYPOTHESIS AND OBJECTIVES

Hypothesis

Ruxolitinib (also known as INCB018424), a JAK1/2 inhibitor, and pracinostat (a histone deacetylase inhibitor; HDACi) are effective and tolerable treatments for patients with myelofibrosis (MF). Combination of these agents in patients with MF can improve the overall clinical response to therapy without causing excessive toxicity.

Objectives

Primary:

- to determine the efficacy/clinical activity of the combination of ruxolitinib with pracinostat as therapy in patients with MF

Secondary:

- to determine the toxicity of the combination of ruxolitinib with pracinostat as therapy in patients with MF

Exploratory:

- to explore time to response and duration of response
- to explore changes in bone marrow fibrosis
- to explore changes in JAK2V617F (or other molecular marker) allele burden or changes in cytogenetic abnormalities

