Pracinostat will be supplied by Helsinn Healthcare SA in 2 strengths: 45 mg and 60 mg. Each 45 mg and 60 mg capsule contains 45 mg or 60 mg of pracinostat (as free base), respectively, and the following inactive ingredients: microcrystalline cellulose, USP/NF (Avicel PH102) and magnesium stearate, USP/NF. Pracinostat capsule size 1: 45 mg are flesh, opaque, hard gelatin capsules; 60 mg are Swedish orange and white, opaque, hard gelatin capsules.

All study medications must be kept in a secure place under appropriate storage conditions. Capsules are packaged in blister packs. Pracinostat capsules should be stored at controlled room temperature, 15°C to 30°C (59°F to 86°F).

Precautions and Risks Associated with the Study Medication Pracinostat

Hematologic: Treatment with pracinostat has been associated with cytopenias including anemia, thrombocytopenia, and neutropenia. The incidence of cytopenias may

increase with increasing doses of pracinostat. Subjects participating in clinical trials of pracinostat should be monitored closely for adverse hematologic affects. The effect of dose reduction on the amelioration of cytopenias has not been established; however prudent clinical management, including supportive care (appropriate use of transfusions and/or hematopoietic growth factors) and dose modification or discontinuation should be followed (see Section 5.1).

Gastrointestinal: Gastrointestinal disturbances, including nausea, vomiting, and diarrhea, have been reported in subjects treated with pracinostat. Standard antiemetic and antidiarrheal medications and appropriate supportive care should be used per normal clinical practice in subjects participating in clinical trials of pracinostat. Pre-existing nausea, vomiting, and diarrhea should be adequately controlled before beginning therapy.

QTc Prolongation/Cardiac: Asymptomatic QTc interval prolongation has been observed during clinical trials of pracinostat. Subjects with a prolonged QTc interval at Screening will not be permitted to participate in clinical trials of pracinostat. Hypokalemia or hypomagnesemia should be corrected prior to pracinostat administration and consideration should be given to monitoring potassium and magnesium in symptomatic subjects (e.g., subjects with nausea, vomiting, diarrhea, fluid imbalance, or cardiac symptoms).

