6.0 CRITERIA FOR RESPONSE

Best overall response will be categorized according to the International Working Group Criteria¹¹:

Complete remission (CR): Requires all of the following in the absence of both transfusion and growth factor support:

- Bone marrow: Age-adjusted normocellularity; <5% blasts; ≤grade 1 MF[†] and
- Peripheral blood: Hemoglobin ≥10 g/dL and <UNL; neutrophil count ≥ 1.0 × 10⁹/L and <UNL;
- Platelet count ≥100 × 10⁹/L and <UNL; <2% immature myeloid cells[‡] and
- Clinical: Resolution of disease symptoms; spleen and liver not palpable; no evidence of EMH

Partial remission (PR):

- Peripheral blood: Hemoglobin ≥10 g/dL and <UNL; neutrophil count ≥1 × 10⁹/L and <UNL; platelet count ≥100 × 10⁹/L and <UNL; <2% immature myeloid cells and
- Clinical: Resolution of disease symptoms; spleen and liver not palpable; no evidence of EMH or
- Bone marrow: Age-adjusted normocellularity; <5% blasts; ≤grade 1 MF[†], and peripheral blood: Hemoglobin ≥8.5 but <10 g/dL and <UNL; neutrophil count ≥1 × 10⁹/L and <UNL; platelet count ≥50, but <100 × 10⁹/L and <UNL; <2% immature myeloid cells[‡] and
- Clinical: Resolution of disease symptoms; spleen and liver not palpable; no evidence of EMH

Clinical improvement (CI): The achievement of anemia, spleen or symptoms response without progressive disease or increase in severity of anemia, thrombocytopenia, or neutropenia[§]

Anemia response	Transfusion-independent patients: a ≥2.0 g/dL increase in hemoglobin level Transfusion-dependent patients: becoming transfusion-independent [¶]
Spleen response [#]	A baseline splenomegaly that is palpable at 5-10 cm, below the LCM, becomes not palpable** or

	A baseline splenomegaly that is palpable at >10 cm, below the LCM, decreases by $\geq 50\%^{**}$
	A baseline splenomegaly that is palpable at <5 cm, below the LCM, is not eligible for spleen response
Symptoms response	A $\geq 50\%$ reduction in the MPN-SAF TSS ^{††}

Progressive disease:

- Appearance of a new splenomegaly that is palpable at least 5 cm below the LCM or
- A $\geq 100\%$ increase in palpable distance, below LCM, for baseline splenomegaly of 5-10 cm or
- A 50% increase in palpable distance, below LCM, for baseline splenomegaly of >10 cm or
- Leukemic transformation confirmed by a bone marrow blast count of $\geq 20\%$ or
- A peripheral blood blast content of $\geq 20\%$ associated with an absolute blast count of $\geq 1 \times 10(9)/L$ that lasts for at least 2 weeks

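### The response rate counts responses reached on ruxolitinib alone, and Section 8.0 plans no analysis of responses gained or lost after pracinostat is added

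*Combined protocol and SAP*

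**What the plan says.** - **Hypothesis (Section 1.0).** "Combination of these agents in patients with MF can improve the overall clinical response to therapy without causing excessive toxicity".
- **Endpoint (Section 8.0).** "Primary Endpoint is the objective response rate (ORR), defined as a clinical improvement (CI), partial remission (PR), and complete remission (CR"). Section 6.0 adds: "Best overall response will be categorized according to the International Working Group Criteria".
- **Who counts (Section 8.0).** "All subjects meeting the eligibility criteria that have signed a consent form and have begun treatment will be evaluable for response". Having received pracinostat is not a condition.
- **Sequence (Section 8.0).** "Initially patients will receive ruxolitinib alone for the first 3 cycles"; the combination starts at cycle 4. Section 5.0 explains the delay: ruxolitinib usually reaches its maximum benefit within 3 months. For patients already on ruxolitinib at entry, earlier time on the drug counts toward the three cycles.
- **Baseline (Section 6.0, footnote on progressive disease).** Examination and imaging baselines are pretreatment values, not values measured after treatment. No section resets the baseline when pracinostat starts.
- **Futility monitoring (Section 8.0).** "the primary endpoint of interest is the objective response (OR) rate at the end of 6 treatment cycles". The target is 50%, and no ruxolitinib-alone rate is given as a reference.
- **Planned analyses (Section 8.0).** One ORR with a 95% credible interval, generic frequency tables, and Kaplan-Meier curves of time to response (from registration) and duration of response (from first response).
- **Assessments (Section 5.6).** Response after cycles 3 and 6, then every 6 cycles. The spleen is measured by examination in each of cycles 2-7, and the symptom score is collected in each of the first 7 cycles.

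**The concern.** The hypothesis is about what the combination adds. The ORR describes a sequence, ruxolitinib first and pracinostat added later, and by the protocol's own account much of the ruxolitinib benefit should already be present when pracinostat starts.

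The add-on could move the ORR in either direction. It may convert non-responders. It may also cost responses, because clinical improvement must be reached "without progressive disease or increase in severity of anemia, thrombocytopenia, or neutropenia", and Section 3.2 says: "Treatment with pracinostat has been associated with cytopenias including anemia, thrombocytopenia, and neutropenia". Section 2.1 says ruxolitinib too may cause anemia and thrombocytopenia, so a lost response is not attributable to pracinostat by default. A single net figure can hide gains and losses that cancel. At stake is whether the report can describe, even roughly, what happened to response after pracinostat was added.

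**Working it through.** **Step 1. Does a response reached in cycles 1-3 count?** Evaluability starts with treatment, treatment starts with ruxolitinib alone, the category is best overall response, and the baseline is pretreatment. Nothing requires a response to begin, deepen or persist after cycle 4. It counts. Under the futility endpoint at the end of cycle 6, it counts if still present then.

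**Step 2. Would a planned analysis separate the two periods?**
- Overall ORR: no.
- Time to response: shows roughly how many first responses came before cycle 4. Its origin is registration, and patients with prior ruxolitinib start pracinostat at differing times after registration.
- Duration of response: shows losses, but pools responses begun before and after pracinostat.
- Frequency tables: no pairing of earlier with later response is named.

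**Step 3. Reproduce the design.** Futility: stop if Pr(p < 0.5) > 0.95 under beta(1+x, 1+n-x). Toxicity: stop if Pr(p > 0.20) > 0.87 under beta(0.4+x, 1.6+n-x). Example at n = 5: with x = 0 the futility probability is 1 - 0.5^6 = 63/64 = 0.984 (stop); with x = 1 it is 1 - 7/64 = 0.891 (continue). The full boundaries are OR at or below 0, 2, 4, 6 and toxicity at or above 3, 4, 6, 7 at n = 5, 10, 15, 20, as in Table 1. Exact enumeration with independent OR and toxicity and a maximum of 25 reproduces all 16 rows of Table 2 (stop probabilities within 0.005, average sample sizes within 0.1).

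**Step 4. Continuation if pracinostat changes nothing.** Let r be the response rate on ruxolitinib alone, g the share of non-responders who gain a response by cycle 6, and l the share of responders who lose it. Then cycle-6 ORR = r(1-l) + (1-r)g. With g = l = 0 and no dropout, ORR = r. The values of r are assumptions.

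| r | Stop early, toxicity 10% | Not stopped | Stop early, toxicity 20% | Not stopped |
|---|---|---|---|---|
| 30% | 0.687 | 0.313 | 0.737 | 0.263 |
| 40% | 0.354 | 0.646 | 0.457 | 0.543 |
| 50% | 0.131 | 0.869 | 0.270 | 0.730 |
| 60% | 0.044 | 0.956 | 0.197 | 0.803 |

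**Step 5. One ORR, two histories.** Suppose 13 of 25 respond at cycle 6 (95% credible interval 33.4%-70.1%; beta(1,1) prior assumed here and below).
- 13 run-in responders all kept, 0 of 12 others gained: 13 + 0 = 13. Gain rate interval 0.2%-24.7%.
- 10 of 13 kept, 3 of 12 gained: 10 + 3 = 13. Gain rate interval 9.1%-53.8%.

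The ORR is identical in both.

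**Step 6. What could a cycle-3 by cycle-6 table show?** Cycles 1-3 and cycles 4-6 each last 3 x 28 = 84 days, or 12 weeks. Set against the footnotes to Section 6.0:
- Worsening of anemia by hemoglobin must last at least 12 weeks. A fall that begins after pracinostat starts will generally not qualify by the end of cycle 6. The platelet and neutrophil criteria carry no duration rule.
- Transfusion independence needs a 12-week transfusion-free window. A dependent patient last transfused during cycle 1 cannot meet it by the end of cycle 3 but can by cycle 6, so a ruxolitinib effect can appear as a new response.
- Spleen response needs MRI or CT confirmation, which Sections 5.5 and 5.6 do not schedule.
- No marrow is scheduled after cycle 3, so response can be compared as yes/no but not by full category.

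**Step 7. Precision.** With 25 patients, r = 40% and no dropout there are 10 run-in responders and 15 non-responders. Three gains of 15 gives 7.3%-45.6%; two losses of 10 gives 6.0%-51.8%.

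**The case against.** The strongest reply is that this is a matter of interpretation. The lead-in is deliberate and explained in Section 5.0. The sequence and endpoint are stated openly, and a single-arm phase II trial of 25 patients cannot isolate the contribution of one drug. The proposed table would be imprecise, uncontrolled and partly distorted by the 12-week rules. Frequency tables could already give response counts at each visit.

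Most of this stands, and it is why the point is minor. It does not remove the gap: separate counts per visit do not show who gained and who lost, and fixing the baseline and spleen method beforehand prevents choices made after results are seen.

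Three stronger readings are tempting, and the documents do not support them.
- *The trial could declare pracinostat effective on ruxolitinib responses.* Section 8.0 contains no efficacy success rule; its response rule only stops for futility.
- *Every assessment needed to split the IWG response is already scheduled.* Imaging is not. A patient already on ruxolitinib may also start pracinostat soon after registration, with no on-study response assessment before it. Against a study-entry baseline, such a patient is a prior non-responder almost by construction.
- *The table would measure the effect of pracinostat.* Late ruxolitinib responses, the ruxolitinib dose increases allowed in Section 5.1, and cytopenias from either drug cannot be excluded.

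The difference between best overall response (Section 6.0) and response at the end of cycle 6 (Section 8.0) is a separate question and adds no weight here.

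**Conclusion.** The point holds as a minor one. Responses reached on ruxolitinib alone enter the ORR, and no planned analysis shows responses gained or lost after pracinostat starts. The first part follows from the definitions taken together; the plan does not say it outright. The plan's own figures are correct and not in dispute: Tables 1 and 2 depend only on total response, so they are the same whichever drug produced it.

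The size cannot be fixed from the documents. At assumed run-in rates of 30% to 60%, with no gain, loss or dropout, the chance of not stopping early is 31% to 96% at 10% toxicity and 26% to 80% at 20%. These are probabilities of continuing, and say nothing about a claim of benefit.

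**What to change.** Keep the ORR, boundaries, sample size and visits. In Section 8.0:

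1. State that the ORR describes the ruxolitinib-then-add-on sequence and is not by itself evidence of a pracinostat contribution.
2. Prespecify a descriptive cross-tabulation of response (yes/no) at the last assessment before the first pracinostat dose by response after cycle 6.
   - Restrict the main table to patients who were ruxolitinib-naive at entry, for whom the first assessment is the one after cycle 3.
   - Report gains among prior non-responders who start pracinostat and losses among prior responders, each with a 95% credible interval.
   - Show spleen, symptom and anemia components, using the same baseline and method at both points. Label the spleen component as palpation-based unless MRI or CT is available.
   - List patients already on ruxolitinib at entry separately, without reading their new responses as gains from pracinostat.
3. State whether the pretreatment baseline in Section 6.0 means before ruxolitinib or at study entry for patients already on ruxolitinib.
4. State the table's limits beside it: the two 12-week effects, cytopenias from either drug, small counts and no control group.

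The cost is a few sentences and one descriptive table. Restricting the main table to ruxolitinib-naive patients makes its counts smaller than those in Step 7.

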
2.4 Rationale for combining ruxolitinib and pracinostat as therapy for MF

The rationale for the use of histone modifiers in MF relies on the fact that both JAK2 as well as JAK2V617F can translocate to the cell nucleus and phosphorylate specific lysine residues at histone H3 (H3Y41). The affinity of the transcriptional repressor heterochromatin protein 1 α (HP1 α) for histone H3 depends on the phosphorylation status of H3Y41. Phosphorylation of H3Y41 decreases the affinity of H3 to HP1 α . JAK2 inhibitors such as TG101209 or AT9283 abrogate nuclear H3Y41 phosphorylation,

which increases chromatin-bound HP1 α in cells, thus leading to repression of HP1 α -regulated genes such as Imo2. Of note, Imo2 is involved in leukemogenesis. Thus, the JAK2-H3Y41-HP1 α pathway links JAK2 kinase activity to histone modifications, aberrant gene expression and leukemogenesis, thus providing the rationale for the use of agents that target histone modifications in combination with JAK2 inhibitors to more thoroughly suppress JAK2V617F signaling in JAK2-driven malignancies. Clinically, then, one might expect synergism of the two medication in terms of improving further the number of patients with clinically relevant reduction in organomegaly and MF-related systemic symptoms, possibly for a longer duration of time. In addition, it is possible that addition of an HDACi would bring additional benefits to patients, like improvement in blood cell count or improvement in bone marrow fibrosis.

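### The hypothesis is improved response, but Section 8.0 has only an unsourced 50% futility threshold and a final ORR, so the plan as written cannot show improvement over ruxolitinib alone

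*Combined protocol and SAP*

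**What the plan says.** Section 1.0 states the hypothesis: "Combination of these agents in patients with MF can improve the overall clinical response to therapy without causing excessive toxicity". It names no comparator. Section 2.4 supplies one by implication, expecting synergism with JAK2 inhibition, "improving further the number of patients with clinically relevant reduction in organomegaly and MF-related systemic symptoms". Section 5.0 gives every patient three months of ruxolitinib alone (earlier ruxolitinib time counts) and then adds pracinostat, on the ground that ruxolitinib's benefit is usually at its maximum by then.

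Section 8.0 is single-arm: "A total of 25 patients will be enrolled from MDACC". The primary endpoint is CR, PR or CI by IWG criteria. For efficacy monitoring, "The target response rate is 50% and the following futility stopping rule will be applied"; the rule stops treatment if "there is more than 95% chance that the OR rate is less than 50" percent, "with a beta (1,1) prior distribution". At the end, "The objective response rate (ORR) will be estimated along with the Bayesian 95% credible interval". No success criterion and no comparison are specified.

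Sections 2.1 and 2.2 describe ruxolitinib's spleen and symptom benefit in words and give survival hazard ratios. They give no IWG response rate. The only single-agent IWG figure is for pracinostat in Section 2.3, 2 of 22 patients. The notes to Section 6.0 refer spleen baselines to the pretreatment value. Section 5.6 schedules response assessments after cycle 3 and after cycle 6, but the analysis plan makes no use of the pair.

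**The concern.** The question that motivates the trial is what pracinostat adds to ruxolitinib. A patient whose spleen responded to ruxolitinib during the lead-in still counts as a responder afterwards, because the reference value predates both drugs. The ORR therefore mixes ruxolitinib's own effect with any added effect, and nothing in Section 8.0 separates them.

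The 50% target does not fill the gap, because the documents do not say whether it lies above, at or below what ruxolitinib achieves alone on this endpoint. At stake is the conclusion: a trial that runs to 25 patients with an ORR around the target could be reported as supporting the hypothesis when the data are equally compatible with no contribution from pracinostat.

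**Working it through.** **Inputs from Section 8.0.** OR rate prior Beta(1,1); stop if Pr(p < 0.5 | data) > 0.95; looks at 5, 10, 15 and 20 patients; maximum 25; toxicity boundaries from Table 1; OR and toxicity independent. **Assumed, because the documents do not give it:** a ruxolitinib-alone IWG response rate of 0.30, 0.40, 0.50 or 0.60.

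**Step 1: reproduce Table 1.** With x responders in n patients the posterior is Beta(1+x, 1+n−x). The largest x that triggers stopping:

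| n | x | Pr(p<0.5) at x | Pr(p<0.5) at x+1 |
|---|---|---|---|
| 5 | 0 | 0.984 | 0.891 |
| 10 | 2 | 0.967 | 0.887 |
| 15 | 4 | 0.962 | 0.895 |
| 20 | 6 | 0.961 | 0.905 |

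These are the printed OR boundaries.

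**Step 2: reproduce Table 2.** An exact binomial recursion over the four looks with both rules gives early-stopping probabilities of 0.687, 0.354, 0.131 and 0.044 at true OR 0.3, 0.4, 0.5 and 0.6 with true toxicity 0.1. The table prints 0.69, 0.35, 0.13 and 0.04. All 16 rows agree. The computation is sound; the issue is what 50% stands for.

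**Step 3: a combination that adds nothing.** Its true OR rate equals the ruxolitinib-alone rate. The futility-only stopping probability is the sum over the four looks. At 0.50 this is 0.0312 + 0.0391 + 0.0264 + 0.0180 = 0.115, so it passes all looks with probability 1 − 0.115 = 0.885. Adding the toxicity rule at true toxicity 0.1 (probability 0.019 of a toxicity stop) gives 0.885 × 0.981 = 0.87.

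| Assumed ruxolitinib-alone rate | Passes all futility looks | Same, with toxicity rule (true toxicity 0.1) |
|---|---|---|
| 0.30 | 0.32 | 0.31 |
| 0.40 | 0.66 | 0.65 |
| 0.50 | 0.885 | 0.87 |
| 0.60 | 0.97 | 0.96 |

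**Step 4: what one final result can mean.** Suppose 15 of 25 respond (60%). The posterior is Beta(16, 11), with 95% credible interval 0.406 to 0.766. The probability that the true rate exceeds the ruxolitinib-alone rate is:

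| Assumed ruxolitinib-alone rate | Pr(p > rate), given 15/25 |
|---|---|
| 0.30 | 0.999 |
| 0.40 | 0.978 |
| 0.50 | 0.837 |
| 0.60 | 0.479 |

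The same data run from near certainty of improvement to roughly a coin toss, depending on a number the plan does not state.

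**The case against.** The strongest reply is that the plan never claims a comparison. The primary objective is to determine the activity of the combination, an ORR with a credible interval does that, and single-arm phase II trials of this size are usual. Section 1.0 names no comparator, and the word pointing to one in Section 2.4 is rationale, not an estimand. This stands in part: if estimation is all that is intended, the remedy is to say so. The hypothesis as worded, with the lead-in design, still invites the added-benefit reading.

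Four stronger readings are tempting, and the documents do not support them.

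- A reader might infer that 50% is the test of the hypothesis. It is called a target but works only as a futility threshold. At 25 patients, 9 responders (36%) would not cross the same criterion (posterior 0.916), while 8 would (0.962). Not being stopped is much weaker than reaching 50%.
- A reader might infer that a combination adding nothing will nearly always appear to meet the target. At a true rate of 50%, the chance of completing with at least 13/25 is 0.49, and 13/25 is not a criterion in the plan. Completion also depends on toxicity: Table 2 implies 1 − 0.27 = 0.73 at true OR 0.5 and toxicity 0.2.
- A reader might infer that the rule wrongly stops combinations that help. A rise from 30% to 40% is stopped for futility with probability 0.34, but 30% is an assumption, Table 2 already shows 0.35 at a true OR of 0.4, and a sponsor seeking 50% may accept that.
- A reader might infer that the trial has no ruxolitinib-alone reference. The cycle 3 assessment in Section 5.6 provides one within patients; it is simply not analyzed.

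**Conclusion.** The point holds in this limited form. The plan can estimate the ORR of ruxolitinib followed by the combination and can stop for a rate clearly below 50%. It cannot, as written, show that pracinostat improves response over ruxolitinib alone, and neither passing futility nor an ORR near 50% should be read that way. The probabilities above rest on an assumed ruxolitinib-alone range of 30 to 60%; their spread shows how much the interpretation depends on an unstated number and is not a demonstrated error in the plan. Tables 1 and 2 are correct. The comparator is inferred from Sections 2.4 and 5.0, not stated in the hypothesis.

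**What to change.** Keep Table 1 and the futility rule unchanged, and state where the 50% comes from. Then:

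- **(a) Limit the claim.** State in Sections 1.0 and 8.0 that the trial estimates the ORR of ruxolitinib followed by the combination, and that passing futility or an ORR of 50% or more will not be reported as improvement over ruxolitinib alone.
- **(b) Show the dependence on the benchmark.** Beside the ORR and its interval, report Pr(p(OR) > p(S) | data), where p(S) is the ruxolitinib-alone rate, over a prespecified range such as 0.3 to 0.6. Use a sourced benchmark with its own Beta prior only if one exists on the same IWG definition and time point. Reference 5 (107 ruxolitinib patients) is cited for survival and is not shown to report this endpoint.
- **(c) Use the in-trial reference.** From the assessments already scheduled after cycles 3 and 6, report the ORR at each and the proportion of cycle-3 non-responders who newly respond by cycle 6. Describe this as supportive, since late responses to ruxolitinib cannot be separated from responses to pracinostat. Say what the pretreatment baseline is for patients already on ruxolitinib at entry.

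This costs wording and a few summaries from data already planned, with no change to enrollment, visits or monitoring. The downside is a more modest conclusion and wider stated uncertainty.
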